# AUC0-48h on change in dyspnoea by VAS score

Analysis will be performed only for patients with VAS score at screening different from 100 or missing.

1.0/30/10/2018 Page 20 of 28

AUC0-48h on change in dyspnoea by VAS score will be summarized by treatment group by means of descriptive statistics.

Comparison between treatment groups will be performed by means of an ANCOVA model with AUC0-48h on change in dyspnoea by VAS score as dependent variable, treatment, centre, gender, baseline cTnT (normal  $\leq$ URL, abnormal  $\geq$ URL) and atrial fibrillation (Yes/No) as fixed effects and baseline dyspnoea as covariate.

The number of patients and the number of patients considered in the model will be provided by treatment. P-values of the fixed effects and covariate will also be presented.

The adjusted means for treatments and the 95% CIs will be presented. The differences between the adjusted means for Istaroxime groups versus Placebo will be calculated with the 95% CIs and p-values.

# **BNP**

BNP and change from baseline will be summarized at each timepoint by treatment group by means of descriptive statistics.

Comparison between treatment groups will be performed by means of an ANCOVA model with change from baseline in BNP at 24 hours as dependent variable, treatment, centre, gender, baseline cTnT (normal <URL, abnormal ≥URL) and atrial fibrillation (Yes/No) as fixed effects and baseline BNP as covariate

The number of patients and the number of patients considered in the model will be provided by treatment. P-values of the fixed effects and covariate will also be presented.

The adjusted means for treatments and the 95% CIs will be presented. The differences between the adjusted means for Istaroxime groups versus Placebo will be calculated with the 95% CIs and p-values.

# Patients with hospital readmissions or emergency visits for cardiovascular reasons within Day 30

The number and percentage of patients with hospital readmissions or emergency visits for cardiovascular reasons within Day 30 will be summarized by treatment groups using descriptive statistics.

# Patients with episodes of worsening heart failure during the hospitalization

The number and percentage of patients with episodes of worsening heart failure during the hospitalization will be summarized at Days 2, 3 and 4 by treatment groups using descriptive statistics.

# Length of hospitalization

Length of hospitalization and the number days of hospitalization after day 4 will be summarized by treatment group using descriptive statistics.

1.0/ 30/10/2018 Page 21 of 28

# 7.8 ANALYSIS OF SAFETY

Analysis will be performed on Safety population.

### Adverse events

Pre-treatment AEs and TEAEs will be presented separately. Pre-treatment AEs will be presented in the listings only.

The number of treatment-emergent AEs, SAEs, ADRs, AEs leading to discontinuation and AEs leading to death, and the number and the percentage of patients experiencing treatment-emergent AEs, SAEs, ADRs, AEs leading to discontinuation and AEs leading to death will be summarised by treatment group.

AEs will be coded using the MedDRA dictionary (version 16.0). The SOCs and PTs will be used for tabulation. The number of AEs and the number and the percentage of patients with at least one AE will be presented by SOC and PT for treatment-emergent AEs, SAEs, ADRs, AEs leading to discontinuation and AEs leading to death by treatment group.

# Vital signs

Vital signs and change from pre-dose will be summarised by treatment group at each timepoint by means of descriptive statistics.

# **Biomarkers**

NT-proBNP and cTNT and increase of cTnT will be summarised by treatment group at screening visit and at all timepoints during the study by means of descriptive statistics.

The number and percentage of patients with a percent change from pre-dose in cTnT >50% and >20% will be summarized at each post-dose timepoints by treatment group.

The number and percentage of patients with a normal cTnT value (<14 ng/L) at screening and with a percent change from pre-dose in cTnT >50% and the number and percentage of patients with an abnormal value of cTnT (≥14 ng/L) at screening and with a percent change from pre-dose in cTnT >20% will also be summarized at each post-dose timepoints by treatment group.

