6.2 Safety Endpoints

The following safety endpoints will be assessed during treatment and the post-treatment/follow-up periods:

- Incidence of adverse events;
- Change in vital signs (including body temperature and dyspnoea);
- Change in 12-lead ECG parameters;
- Incidence of clinically or hemodynamically significant episodes of supraventricular or ventricular arrhythmias detected by continuous ECG dynamic monitoring;
- Change in laboratory parameters (hematology, blood chemistry and urinalysis);
- Change in renal function;
- Change in cTnT;
- Incidence of cTnT elevation relative (>50% or >20% relative increase over the cTnT levels at baseline, for patients with cTnT basal levels at baseline < or ≥ of the 99% URL (upper reference levels, as defined for the Roche hs test in patients with normal renal function, eGFR ≥ 85 ml/min); in patients with eGFR below this value, the renal function variations must be considered in evaluating the significance of the cTnT changes);

• Mortality at Day 30.

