# The safety endpoints are:

- Incidence of Adverse Events (AEs);
- Change in vital signs;
- Change in 12-lead Electrocardiogram (ECG) parameters;
- Incidence of clinically or hemodynamically significant episodes of supraventricular or ventricular arrhythmias detected by continuous ECG dynamic monitoring;
- Change in laboratory parameters (hematology, blood chemistry and urinalysis);
- Change in renal function (Estimated glomerular filtration rate (eGFR));
- Change in cTnT;
- Incidence of cTnT elevation relative (>50% or >20% relative increase over the cTnT levels at baseline, for patients with cTnT basal levels at baseline < or ≥ of the 99% Upper Reference Limit (URL, as defined for the Roche hs test to be 14 ng/L) respectively;
- Mortality at Day 30.

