# Incidence of cTnT elevation relative

Percent change from baseline in cTnT will be calculated using the following formula at all post-dose timepoints (3h, 6h, 12h, 24h, 48h, 72h):

% change from baseline = 100 \* (cTnt at timepoint – cTnT at screening) / cTnT at screening

The following categories will be defined at each timepoint:

- For patients with normal cTnT value (< URL) at screening:
  - A patient will be classified as a "patient with a percent change from baseline in cTnT >50%" if the percent change from baseline in cTnT is greater than 50% (percent change from baseline in cTnT > 50%);
- For patients with abnormal cTnT value ( $\geq$  URL) at screening:

1.0/30/10/2018 Page 15 of 28

A patient will be classified as a "patient with a percent change from baseline in cTnT >20%" if the percent change from baseline in cTnT is greater than 20% (percent change from baseline in cTnT > 20%);

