# 7.3 INTERIM ANALYSIS AND SEQUENTIALITY OF ANALYSES

After the completion of cohort I, a safety interim analysis will be performed and the Data Monitoring Committee (DMC) members will evaluate the incidence of cTnT elevation. At interim analysis, the DMC may recommend to do not proceed with the next cohort if the incidence of cTnT elevation is found to be statistically significantly higher on the istaroxime dose than on placebo, or if this difference is deemed to be clinically relevant. Consequently, the clinical study will be prematurely terminated.

Randomization data and datasets needed to conduct the interim analysis will be given by an independent statistician to the DMC statistician. The DMC will be unblinded when performing the interim analysis.

During the interim analysis, DMC members will analyze and discuss the results in closed sessions. The DMC is required to keep confidential and undisclosed until study conclusion: i) these discussions, ii) the detailed minutes thereof, and iii) the interim analysis results.

For the primary endpoint, the primary comparison will be  $0.5 \mu g/kg/min$  dose of istaroxime versus placebo at 24 hours. Highest dose of istaroxime (1.0  $\mu g/kg/min$ ) versus placebo will be tested as a secondary comparison.

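### The SAP text defines and tabulates cTnT elevation only timepoint by timepoint; it pre-specifies no patient-level incidence and no test, although the safety endpoint and the interim rule refer to a single incidence

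*SAP*

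**What the plan says.** **Endpoint.** Protocol 6.2 lists "Incidence of cTnT elevation relative (>50% or >20% relative increase over the cTnT levels at baseline", with the 50% threshold for patients whose baseline is below the 99% URL and the 20% threshold for those at or above it. SAP 3.2.2 repeats this and fixes the URL, "as defined for the Roche hs test to be 14 ng/L) respectively". Neither gives a time window.

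**Derivation.** SAP 6.4 has a paragraph named after the endpoint. It computes percent change at six post-dose times (3, 6, 12, 24, 48 and 72 h) and then states: "The following categories will be defined at each timepoint".

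**Tables.** SAP 7.8 (Biomarkers) plans two sets of counts:
- Not split by baseline category: "patients with a percent change from pre-dose in cTnT >50% and >20% will be summarized at each post-dose timepoints by treatment group".
- Matched to the endpoint: patients below 14 ng/L at screening with a rise above 50%, and patients at or above 14 ng/L with a rise above 20%. These "will also be summarized at each post-dose timepoints by treatment group".

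SAP 7.9 adds no other analysis.

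**Interim rule.** Under SAP 7.3 the board may recommend not opening the next cohort "if the incidence of cTnT elevation is found to be statistically significantly higher on the istaroxime dose than on placebo", or if the difference is judged clinically relevant. Protocol 16.3 has the same two limbs. Neither section names a timepoint, a patient-level definition or a test.

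**The concern.** The endpoint and the interim rule each speak of one incidence per arm. The derivation and tables give a series of single-time percentages, each the proportion elevated at that sample. A patient elevated only at 6 h and another elevated only at 48 h never appear in the same count.

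The SAP does use patient-level incidence elsewhere: the adverse event tables in SAP 7.8 count patients with at least one event. The one safety variable tied to a named interim criterion is not treated in that way.

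Two things are at stake. At the interim, the quantity to be compared, and how to compare it, would be settled by people who are already unblinded. In the final report, a SAP followed as written would not state how many patients on each arm met the endpoint.

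**Working it through.** The documents give no cTnT event rate, effect size or power, so there is no stated figure to reproduce. The rates and correlations below are assumptions.

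**Inputs**
- Six post-dose times (SAP 6.4).
- Two baseline categories, each with its own threshold (Protocol 6.2; SAP 3.2.2).
- Cohort I: 40 istaroxime, 20 placebo (Protocol section 3; 60 × 2/3 = 40, 60 × 1/3 = 20).
- Two-sided alpha of 0.05 (SAP 7.4).

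**1. What the planned tables contain.** The endpoint-matched table has 6 times × 2 categories = 12 proportions per arm; the unsplit table has another 12. The two categories do not overlap, so their counts can be added at each time. That leaves six own-threshold proportions per arm and still no count across time.

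**2. Can the six proportions be turned into an incidence?** Write p_t for the proportion elevated at time t. Whatever the dependence between times,

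max(p_t) ≤ P(elevated at any time) ≤ min(1, Σ p_t).

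With the same rate at all six times:

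| Assumed rate at each time | Lower bound | Upper bound |
|---|---|---|
| 5% | 5% | 6 × 5% = 30% |
| 10% | 10% | 6 × 10% = 60% |
| 20% | 20% | min(100%, 6 × 20%) = 100% |

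**3. Narrower values under a correlation model.** I simulated a latent normal variable with AR(1) correlation between successive samples. Any-time rates:

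| Assumed rate at each time | Correlation 0.8 | Correlation 0.5 |
|---|---|---|
| 10% | about 27% | about 38% |
| 20% | about 46% | about 61% |

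**4. What this can do to the arm comparison.** Suppose the Cohort I table shows 4/40 on istaroxime and 2/20 on placebo at every timepoint, 10% in both arms throughout. Two datasets that fit this table:

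- The same 4 istaroxime patients and the same 2 placebo patients each time. Any-time incidence is 4/40 vs 2/20; Fisher's exact p = 1.00.
- Six different sets of 4 istaroxime patients (6 × 4 = 24) and the same 2 placebo patients each time. Any-time incidence is 24/40 vs 2/20; Fisher's exact p = 0.0002.

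The second dataset is extreme. It is there to show that the planned percentages would be identical in the two cases.

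**5. Baseline.** An any-time flag cannot be derived uniquely until three statements agree. SAP 6.4 computes the change from screening and takes the category at screening. SAP 6.5 sets the cTnT baseline as the mean of the two pre-dose samples. SAP 7.8 takes the category at screening but the change from pre-dose. In addition, Protocol section 9 allows either cTnT or cTnI to be measured locally at screening, so a screening cTnT value may not exist for every patient.

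**The case against.** **The board is not confined to these tables.** Protocol 16.3 and SAP 7.3 give the board's statistician the randomization data and the datasets. The rule has a clinical-relevance limb, the board only recommends, and Protocol section 3 bases escalation on the safety data as a whole. A reader might infer that the board's incidence is never produced. The documents do not support that: it can be computed. What stands is that its definition and test are not pre-specified.

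**The split by URL category hides little.** A reader might infer that elevation is tabulated only within category. SAP 7.8 also plans unsplit counts, and the categories can be summed. The unsplit counts do not apply each patient's own threshold, so they are not the endpoint; but the gap that remains is the one across time.

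**The endpoint wording does not say at any time.** Correct. That is the natural reading of incidence, and it is an inference. No lead timepoint is named either, so the single quantity stays undefined on any reading.

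**Multiple looks.** A reader might infer that six timepoints generally inflate the chance of a false alarm. No per-timepoint test is planned, and the effect depends on the rate. Simulating 40 vs 20 with no drug effect, the chance of at least one timepoint significantly higher on istaroxime (Fisher) is about 3% to 9% at per-timepoint rates of 10% to 30%. At 5% it is only 0.1% to 0.2%, below the roughly 1.5% for a single any-time test. No general claim of inflation is made.

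**Mock-ups.** The SAP's table shells are in a separate file that was not available. A table there cannot be ruled out, but a shell would not replace a definition in SAP 6.4.

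**Conclusion.** The point holds for the SAP text. Elevation is defined and counted only at single timepoints, while the endpoint and the interim rule use one incidence that is neither defined nor given a test. The bounds in step 2 need no assumption beyond the per-timepoint rate: at 10%, the any-time incidence may be 10% to 60%. The narrower 27% to 38% rests on the assumed AR(1) correlations of 0.8 and 0.5.

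This is a gap in pre-specification and in planned reporting. It does not show that the board would lack the figure or would reach a wrong recommendation. It should be corrected, since the endpoint cannot be recovered from the planned counts and the data needed are already collected.

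**What to change.** 1. **SAP 6.4 and 7.8.** Add one patient-level flag: cTnT elevated by the patient's own threshold (above 50% if baseline is below 14 ng/L, above 20% if at or above 14 ng/L) at any post-dose sample from 3 to 72 h. Combine the two categories. Report n/N by arm with the between-arm difference and 95% CI.
2. **Baseline.** Use one baseline for both the category and the change. SAP 6.5 already specifies the mean of the two pre-dose samples; bring SAP 6.4 and 7.8 into line with it.
3. **Missing samples and Day 30.** State how patients with missing samples count. Say that the Day 30 cTnT, which Protocol section 9 collects but SAP 6.4 does not list, is reported separately.
4. **SAP 7.3 and Protocol 16.3.** Name this incidence as the quantity the board reviews and name its test, for example Fisher's exact at two-sided 0.05. The clinical-relevance limb is not affected.
5. Keep the per-timepoint tables as supportive.

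The cost is wording in both documents and one derived variable, with no new data. The headline incidence will be at least as high as any single-timepoint figure when calculated on the same patients, and the report should say so.

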# 24 hours digital ECG Holter

Premature ventricular complexes, ventricular tachycardia, new onset atrial fibrillation and incidence of clinically or hemodynamically significant episodes of supraventricular or ventricular arrhythmias will be summarised by treatment group at screening and Days 1 and 2 by means of descriptive statistics.

**ECG** 

1.0/ 30/10/2018 Page 22 of 28

ECG parameters derived from 12-lead ECG will be summarized by treatment group at screening and Days 1, 2, 3 and 4 by means of descriptive statistics.

# Laboratory parameters

Shift tables presenting the number and the percentage of patients in each bivariate category (screening and Day 3) with regards to investigator's interpretation (normal, Not Clinically Significant (NCS), Clinically Significant (CS), No result (NR)) will be provided for all laboratory parameters (excluding potassium, eGFR, creatinine and creatinine clearance).

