7. STUDY PROCEDURES

♦ Screening period (between Hours -24 to -1)

Within a maximum of 24 hours before administration of study medication (istaroxime or placebo), a medical screening will be performed on all prospective patients to assess suitability for the study. Prior to conducting any study specific procedures, the investigator or his/her designee will explain the study fully to the patient and provide him/her with a copy of the Patient Information Sheet and Informed Consent Document. If the patient is willing to participate in the study, s/he and the investigator or his/her designee will both sign the Informed Consent Document and a copy of the signed document will be kept by the patient.

1) Obtaining of ICF;

- 2) Evaluation of screening inclusion and exclusion criteria;
- 3) Stratification: Atrial fibrillation YES/NO;
- 4) Medical history, demographic/anthropometric data;
- 5) Alcohol and tobacco consumption patterns;
- Medication history (previous and concomitant), including a list of the patient's previous and current intake of vitamins, over-the-counter drugs and herbal products for the last 3 months. Chronic oral treatment with digoxin and other medications (e.g. diuretic and/or vasodilator) will also be recorded;
- 7) Vital signs (including body temperature and dyspnea);
- 8) 12-lead ECG; (Data obtained within 3 hours before the patient signed informed consent form can be accepted.)
- 9) Holter ECG;

- 10) Standard blood chemistry and Standard haematology;
- 11) TSH, T3 and T4;
- 12) Estimated glomerular filtration rate (eGFR);
- 13) Digoxin assay;
- 14) Urinalysis;
- 15) Alcohol breath test (at random, if deemed necessary by the Investigator/designee);
- 16) Serum pregnancy test (beta human chorionic gonadotropin [β-hCG]) for females of childbearing potential;
- 17) Echocardiography;
- 18) Serum creatinine clearance;
- 19) Human Immunodeficiency Virus, Hepatitis B and Hepatitis C tests;
- 20) Adverse events monitoring (after obtaining informed consent);
- 21) BNP, NT-proBNP and cTnT;

♦ Treatment period (Day 1)

- 1) Confirm eligibility;
- 2) Randomization of patients (after eligibility has been confirmed);
- 3) Insertion of multiple lumen intravenous catheter (or administration via peripheral vein);
- 4) Start istaroxime or placebo infusion (date and time of infusion start must be recorded in the CRF);
- 5) cTnT (at pre-dose in two samples, 3, 6, 12, 24, 48 and 72 hours after start of infusion);

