- 8) cTnT (50% or 20% relative increase over the basal cTnT levels, respectively for patients with cTnT basal levels < or ≥ of the 99% URL (upper reference levels, as defined for the Roche hs test, in patients with normal renal function, eGFR≥85 ml/min); in patients with eGFR below this value, the renal function variations must be considered in evaluating the significance of the cTnT changes);
- 9) NT pro-BNP
- 10) Metabolites
- 11) Echocardiography;
- 12) Concomitant medication monitoring (including chronic medication must be recorded in the CRF);
- 13) Adverse Events monitoring

Evaluations on Day 3 include:

- 1) Vital signs (including arterial oxygen saturation and dyspnea)
- 2) 12-Lead ECG (single ECGs)
- 3) Stop 24-hour Holter ECG
- 4) Standard hematology;
- 5) Standard blood chemistry;
- 6) Serum Potassium levels;

- 7) 24-h urine collection for measurement of istaroxime metabolites and urinary creatinine for the calculation of creatinine clearance;
- 8) Calculation of eGFR;
- 9) NT-proBNP
- 10) cTnT;
- 11) Metabolites;
- 12) Echocardiography;
- 13) Adverse events monitoring;
- 14) Concomitant medication monitoring (including chronic medication must be recorded in the CRF)

Evaluations on Day 4 include:

- 1) cTnT and NT-proBNP (at 72 hours after start of infusion)
- 2) Vital signs (including arterial oxygen saturation and dyspnoea)
- 3) Physical examination (HF signs included)
- 4) 12-lead ECG
- 5) Adverse events monitoring
- 6) Concomitant medication monitoring (including chronic medication)
- 7) Metabolites (at 72 hours after start of infusion)
- 8) Serum potassium and creatinine levels for calculation of eGFR
- 9) Creatinine clearance

♦ Follow-up period and visit (Day 5 to Day 30)

During the follow-up period the Investigator/designee will make every effort to establish patient outcomes.

Evaluations on Day 30 (follow-up visit) include:

- 1) Vital signs (including arterial oxygen saturation and dyspnoea);
- 2) 12-lead ECG in triplicate;
- 3) Calculation of eGFR;
- 4) Standard hematology;
- 5) Standard blood chemistry;
- 6) NT-proBNP;
- 7) cTnT;
- 8) Urine pregnancy test (β -HCG) for females of childbearing potential;
- 9) Urinalysis;

- 10) Physical examination (HF signs included);
- 11) Adverse events monitoring;
- 12) Concomitant medication monitoring (including chronic medication).

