9. SAFETY ASSESSMENTS

- 1. AEs will be monitored throughout the study (i.e. from the time of signature of informed consent to treatment end + 30 days);
- 2. Physical examination (HF signs included) at screening, baseline, on study Day 4 or at discharge, and on study Day 30 during the follow up visit;
- 3. Vital signs (HR, BP, respiratory rate, body temperature and dyspnoea)) will be measured at screening, (concomitantly to hemodynamic measurements) during the pretreatment period, at 3, 6, 12, and 24 hours after infusion start, and then on study Day 3 and Day 4 or at discharge, and on study Day 30 during the follow up visit;
- 4. 12-lead ECG (HR, RR and PR intervals, QRS duration, QTc, rhythm, ectopy, ischemic changes) will be recorded and locally analyzed at screening and on study Day1, Day2, Day 3 and Day 4 or at discharge, and on study Day 30 during the follow up visit;
- 5. Continuous Holter monitoring will take place during screening, treatment (Day 1), and Day 2.
- 6. Blood samples will be collected and sent to the local laboratory during screening, 48 hours after infusion starts and on Day 30 to measure the following safety parameters:

Protocol N°: CVT-CV-002 42

- a) Hematology: red blood cell (RBC) count, Hb, hematocrit (Hct), white blood cell (WBC) count, differential WBC count, platelet count;
- b) Blood chemistry: electrolytes (Na⁺, K⁺, Ca⁺⁺, Cl⁻), albumin, total protein, glucose, creatinine, eGFR, BUN (blood urea nitrogen), alkaline phosphatase, ALAT, ASAT, total and conjugated bilirubin, gamma glutamyl transferase (γ-GT), total cholesterol, triglycerides;
- 7. Blood samples for creatinine will be collected by the local laboratory at each time after infusion start
- 8. cTnT or cTnI will be measured locally during screening. While cTnT only will be measured by the central laboratory, at pre-dose in two samples, at 3, 6, 12, 24, 48, 72 hours after infusion start or at discharge and at 30days by using the hs test from Roche cobas. Incidence of cTnT elevation (>50% or > 20% relative increase over the basal cTnT levels at baseline, for patients with cTnT levels at baseline < or ≥ of the 99% URL (upper reference levels, as defined for the Roche hs test, in patients with normal renal function, eGFR ≥85 ml/min); in patients with eGFR below this value, the renal function variations must be considered in evaluating the significance of the cTnT changes).

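### SAP 7.8 stops the laboratory shift tables at Day 3, so urinalysis has no scheduled post-baseline result to tabulate, and Day 30 haematology and most Day 30 chemistry enter no laboratory table

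*SAP*

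**What the plan says.** **Endpoint.** The SAP's list of safety endpoints (3.2.2) includes "Change in laboratory parameters (hematology, blood chemistry and urinalysis", and Protocol 6.2 names the same three components. Protocol 6.2 opens with: "The following safety endpoints will be assessed during treatment and the post-treatment/follow-up periods".

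**Analysis.** SAP 7.8 (Laboratory parameters) plans shift tables with the "number and the percentage of patients in each bivariate category (screening and Day 3" as the only visit pair, classified by the investigator's interpretation. The tables "will be provided for all laboratory parameters (excluding potassium, eGFR, creatinine and creatinine clearance". Those four parameters have their own paragraph (Renal function), which summarises them at screening and Days 2, 3, 4 and 30. SAP 6.5 makes screening the laboratory baseline. SAP 7.9 plans no other analysis.

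**Schedule.** Protocol section 7 lists "14) Urinalysis" at screening and urinalysis again at Day 30 (item 9), and at no other visit. The Day 3 list has haematology, chemistry and a "24-h urine collection for measurement of istaroxime metabolites and urinary creatinine for the calculation of creatinine clearance". Protocol section 9, item 6, covers the blood panels: "Blood samples will be collected and sent to the local laboratory during screening, 48 hours after infusion starts and on Day 30".

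**The concern.** The SAP's visit pair and the protocol's schedule do not meet for urinalysis. A shift table needs a value at both visits, and urinalysis has only the first. One of the three components of a listed safety endpoint therefore cannot be produced by the stated rule, while the visit at which it could be produced is left out.

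For haematology and chemistry the rule works, but it uses only one of the two scheduled post-baseline panels. The other, at Day 30, is the only scheduled panel in the follow-up period that Protocol 6.2 includes in the endpoint. The protocol says that pharmacokinetic, efficacy and tolerability studies are still needed to judge the risk of infusing beyond six hours, and safety is a stated objective. A systematic by-arm view of liver enzymes, platelets or haemoglobin at Day 30 is therefore worth having.

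**Working it through.** No sample size, power or error rate is involved, and the plan states no figure to reproduce. The check sets the schedule against the analysis.

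| Laboratory group | Scheduled (Protocol 7 and 9) | Tabulated (SAP 7.8) | Scheduled post-baseline visits tabulated |
|---|---|---|---|
| Urinalysis | Screening, Day 30 | Screening vs Day 3 | 0 of 1 |
| Haematology | Screening, Day 3 (48 h), Day 30 | Screening vs Day 3 | 1 of 2 |
| Chemistry outside the SAP's renal set | Screening, Day 3 (48 h), Day 30 | Screening vs Day 3 | 1 of 2 |
| Potassium, creatinine, eGFR | Several visits, including Day 30 | Screening, Days 2, 3, 4, 30 | Day 30 included |

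**Urinalysis.** Planned patients: 96 + 24 = 120. Patients with a Day 3 urinalysis on the schedule: 0 of 120. The Day 3 urine is a timed collection for metabolites and creatinine, not a urinalysis, and section 9 lists only haematology and chemistry for the 48-hour sample. Every patient would fall in the table's no-result category, or in the Missing category that SAP 7.1 keeps in the denominator.

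**Blood items at Day 30**, counted from Protocol section 9, item 6:

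- Haematology, 6 items: red cells, haemoglobin, haematocrit, white cells, differential, platelets.
- Chemistry, 18 items: sodium, potassium, calcium, chloride, albumin, total protein, glucose, creatinine, eGFR, BUN, alkaline phosphatase, ALAT, ASAT, total bilirubin, conjugated bilirubin, gamma-GT, cholesterol, triglycerides.
- Total: 6 + 18 = 24.
- Summarised at Day 30 under Renal function: potassium, creatinine and eGFR = 3.
- In no Day 30 laboratory table: 24 − 3 = 21, made up of 6 haematology and 15 chemistry items.

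**Was the limit declared?** Protocol 14.2 promises descriptive statistics for laboratory parameters by treatment group and names no visits. SAP 1.1 lists only echocardiographic changes. The renal paragraph carries Day 30, and no reason is given for leaving it out elsewhere.

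**After the fix.** Scheduled post-baseline visits tabulated become 1 of 1 for urinalysis and 2 of 2 for haematology and for chemistry outside the renal set.

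**The case against.** A reader might infer that no Day 30 laboratory result is analysed, or that late laboratory changes are invisible by arm. The documents do not support either reading:

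- Potassium, creatinine and eGFR are part of the chemistry panel and are summarised at Day 30.
- NT-proBNP and cTnT are drawn at Day 30, and SAP 7.8 (Biomarkers) summarises them at all timepoints.
- SAP 7.4 puts all CRF data in listings.
- Protocol 10.1 counts abnormal laboratory results among possible adverse events. Events are followed to 30 days after treatment end and tabulated by treatment group.
- Day 30 is the only scheduled laboratory visit after Day 4, so the gap is one visit.

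All of this stands. What remains missing is a systematic by-arm table of Day 30 values, including those not reported as adverse events.

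It can also be argued that the 48-hour panel is a reasonable choice after a 24-hour infusion. It falls 48 − 24 = 24 hours after infusion end. With the 3 to 4.5 hours that the protocol gives as the half-life of PST2915, that is 24 / 4.5 ≈ 5.3 to 24 / 3 = 8 half-lives; the parent drug's half-life is put at 10 to 20 minutes. Since the protocol fixes no visits, the SAP may be elaborating rather than departing from it. This is fair for the blood panels and is why their part is an improvement and not an error. It does not help urinalysis, which has no 48-hour value.

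Finally, the CRF and the mock-ups (SAP Appendix 1) are separate documents. A Day 3 urinalysis page or a Day 30 shift mock-up cannot be excluded, but neither the protocol nor the SAP mentions one. If either exists, the text still needs to agree with it.

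**Conclusion.** **Urinalysis: wrong as written.** On the protocol schedule, the rule in SAP 7.8 gives a table with no post-baseline results for any of 120 planned patients and leaves the one collected post-baseline urinalysis untabulated.

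**Day 30 haematology and chemistry outside the renal set: a cheap improvement.** 21 of 24 blood items are listed at Day 30 but enter no laboratory table by treatment group, although Protocol 6.2 extends the endpoint into follow-up.

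The laboratory analysis is descriptive, and the primary endpoint and the interim troponin review are unaffected. The conclusion assumes that the visit lists in Protocol section 7 are what is collected, and that the mock-ups follow the SAP text.

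**What to change.** In SAP 7.8 (Laboratory parameters), replace the single visit pair with:

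- Haematology and blood chemistry: shift tables from screening to Day 3 and from screening to Day 30.
- Urinalysis: a shift table from screening to Day 30.

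The existing exclusion of the four renal parameters can stay. Update the mock-ups in Appendix 1 to match.

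The cost is one SAP sentence and a few extra tables to program and check. All the data are already scheduled for collection, so no visit, sample or CRF change is needed.
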